## **I. BACKGROUND AND SIGNIFICANCE**

Alcohol (i.e. ethanol) is one of the most widely used recreational substances by humans and is consumed regularly by much of the U.S. population. Despite the high prevalence of alcohol intake, the metabolic health effects associated with use have not been firmly established. There is a paucity of data from longitudinal studies in humans that examine the metabolic response to routine alcohol consumption in a randomized controlled trial (RCT).

## **II. STUDY RATIONALE AND OBJECTIVES**

This is a novel pilot study to examine, for the first time, the effects of ethanol consumption on fat distribution and testosterone during weight loss in a RCT. Findings from this study would provide insight into an interesting and unanswered question -- does routine alcohol intake exert unfavorable health effects despite the expected beneficial outcomes of caloric restriction and weight loss? This research may provide new knowledge of the metabolic outcomes resulting from alcohol intake and pathways that may be involved leading to potential new therapeutic targets of treatment.

The *objective* of the proposed study is to enroll women with obesity that will undergo a controlled, energy restricted feeding intervention to test the effects of chronic ethanol consumption on adipose distribution and circulating testosterone during weight loss. Women will be randomized to an ethanol-free control group or an ethanol-consuming group, and all will consume 30% energy-restricted diets.

## **III. STUDY POPULATION AND ELIGIBILITY CRITERIA**

### **a. Subjects**

- We will enroll 12 participants (N=7 (Ethanol group) and N=5 (Control group)) using the inclusion and exclusion criteria described below. The Recruitment Core at Pennington Biomedical will recruit the women via listserv emails, community flyers, and health promotion events. We will recruit an ethnically diverse group based on the demographics of Baton Rouge.

### **b. Inclusion criteria**

- Pre-menopausal women only
- 21-40 years of age
- BMI 27-50 kg/m^2 (+ 0.5 will be accepted)
- Must practice and be willing to continue to practice appropriate birth control (defined as a method which results in a low failure rate, i.e., less than 1% per year, when used consistently and correctly, such as double barrier methods [male condom with spermicide, with or without cervical cap or diaphragm], implants, intrauterine contraceptive devices, tubal ligation (surgically sterile), abstinence, or in an established relationship with a vasectomized or same sex partner) during the entire duration of the study

- Must be willing to adhere to all study procedures, including consumption of all study foods and beverages and attendance at all study visits
- Must be willing to eat at least one meal at PBRC 3 times per week on weekdays (excluding holidays)
- Must be willing to consume alcohol
- Must be willing to abstain from alcohol for 8-weeks if randomized to non-alcohol control group.
- Must be a daily, or almost daily drinker, defined as typically consuming at least 8 drinks per week, but no more than 4 per day
- Must be willing to undergo an overnight alcohol test (at home) of ethanol at the proposed dose before enrollment in the study
- Must have access to a device that can be used for video monitoring of compliance (i.e. Skype)
- Must be willing to have your blood stored for future research

c. Exclusion criteria

- Non-drinkers of alcohol
- Habitual binge drinkers, as defined by the consumption of  $\geq 4$  standard drinks per day or  $\geq 28$  drinks per week.
- Self-reported alcoholics or a history of alcoholism
- Have a 1st degree relative with alcoholism
- Any attendance or inpatient stay for alcohol or drug treatment
- Display any characteristics of current or future substance abuse disorders
- Presence of any psychiatric, behavioral, or medical disorder that, in the opinion of the PIs, Co-I, or MI, may interfere with study participation, the ability to adhere to the protocol, or has the potential for increased substance abuse
- Prescription medications that interact with alcohol intake
- Abnormal screening laboratory safety tests
- Smokers
- Diagnosis of Type 1 or 2 diabetes mellitus, cancer, or major organ disease
- Serious digestive disorders
- Conditions that affect metabolism or body weight (i.e. uncontrolled thyroid conditions, bariatric surgery, pregnancy, breastfeeding)
- Partial and/or full hysterectomy
- Hormonal pharmaceutical contraceptives including oral contraception (birth control pills), injectables (Depo-Provera), or the patch (Xulane)
- PCOS
- Use of medications that affect body weight or metabolism (i.e. atypical antipsychotics, weight loss medications).
- Not willing to store biospecimens for future use

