#### 8-Week Dietary Intervention

Participants will be provided all meals that are prepared by the PBRC metabolic kitchen (5-day meal rotation) and given both verbal and written instructions as to the consumption of the

food. On weekdays, at least one meal (i.e. breakfast, lunch, or dinner) will be consumed at PBRC 3 times per week, (excluding holidays), whereas the other weekday meals will be packaged for takeout. In addition, alcohol, weekend, and holiday meals will be packaged for takeout. Participants' energy requirements will be determined from their estimated resting metabolic rate (RMR), calculated via the Mifflin-St. Jeor formula, with an activity factor of 1.5. The energy requirements will then be multiplied by 0.70 so that all participants will restrict energy needs by 30% compared to weight maintenance. Each group (control and ethanol) will have the same 30% reduction in calories and will consume the same percentage of each traditional macronutrient (20% protein, 50% carbohydrate, and 30% fat). The ethanol group will consume a 30% energy restriction diet that will also include ~2.5 standard drinks, or 35 grams of ethanol, administered as 80-proof distilled spirits (e.g. 80 proof gin, rum, vodka, whiskey, or tequila). In the United States, one "standard" drink contains roughly 14 grams of pure alcohol. Caloric differences between the spirits will be accounted for by being administered on specific days of the meal rotation so that the appropriate mixers are provided. The remaining calories (Mifflin-St. Jeor formula, with an activity factor of 1.5 multiplied by 0.70 minus the ~240 kcals from ethanol) will be consumed as 20% protein, 50% carbohydrate, and 30% fat. The control group will consume these ~240 kcal as included in the aforementioned macronutrient percentages (20% protein, 50% carbohydrate, and 30% fat).

Participants will be asked to have an in-clinic check in once per week when coming for their in-house meal. At this check a metabolic weight will be obtained, adverse events and changes in medication will also be assessed. The ethanol group will be also be administered the alcohol-related questionnaires.

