**Table 2. Potential Risks and Efforts to Minimize the Risks to Human Subjects**

Procedure	Potential Risks	Efforts to Minimize the Risks
Ethanol (alcohol) Consumption	
Alcohol intake is associated with a variety of health risks, including high blood pressure, liver disease, impaired cognitive function, weakened immune system, and certain types of cancers. Other risks include drowsiness, malaise, mood and behavior changes, depression, headaches, impaired coordination and judgment, and the potential for addiction and dependency. Drinking alcohol also increases the risk of short-term harms, including motor vehicle accidents and injuries.
	
Before enrolling in the study, several measures will be conducted to minimize risks including the following: stringent inclusion/exclusion criteria; SASSI and MAST substance abuse screening questionnaires, a diagnostic interview by a trained behavioral psychologist, and an overnight alcohol test. Additional safeguards and alcoholism screening tools will be implemented frequently throughout the duration of the study. To reduce the risks of alcohol-related harms, participants will be instructed to consume the alcohol over the course of a couple hours at home (not strictly before bedtime) and not while driving or operating machinery. Participants will also report any adverse events or undesirable changes in mood or behavior throughout the duration of the study. Participants will be monitored for non-compliance, as the consumption of additional alcoholic drinks beyond what is required for the study may exacerbate the risks associated with alcohol use.

Blood Draws (Fasting)	Bruising, bleeding, pain, and infection pose minimal risks.	Trained phlebotomists and personnel will use sterile technique.

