- All serious adverse events will be immediately reported to the PIs. The PIs and designated research team will generate a serious adverse event report. The report will include a description of the event, when and how it occurred, as well as any official chart records or documentation to corroborate the event.
- The serious adverse events will be reported to the Medical Investigator at an expedited ad hoc meeting.
- The report will be then immediately forwarded to the IRB (<5 days of the event).

e) Annual safety reports. Based on the documentation from the DSM committee meetings compiled by the Independent Monitor, the study coordinator will prepare a report. A statement reflecting the results of the reviews with the Independent Monitor will be sent to the IRB. This report will include a list of adverse events and will address: (1) whether adverse event rates are consistent with pre-study assumptions; (2) reasons for dropouts from the study; (3) whether all participants met entry criteria; (4) whether continuation of the study is justified on the basis that additional data is needed to accomplish the stated aims of the study; and (5) conditions whereby the study might be terminated prematurely.

f) Stopping Rules - This study will be stopped prior to its completion if: (1) the intervention is associated with adverse effects that call into question the safety of the intervention; (2) difficulty in study recruitment or retention will significantly impact the ability to evaluate the study endpoints; (3) any new information becomes available during the trial that necessitates stopping the trial; or (4) other situations occur that might warrant stopping the trial. Data on subject accrual and completion rates will be synthesized and evaluated annually to determine if the study should be terminated. These data will be reviewed by the study PIs, with consultation from the study biostatistician.

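### Do the inclusion and exclusion lists leave eligibility undecided for a woman who drinks exactly 4 drinks a day?

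*Protocol*

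**What the plan says.** Section III.b (Inclusion criteria) asks for a daily or almost daily drinker, which it defines as "typically consuming at least 8 drinks per week, but no more than 4 per day". Read literally, 4 a day is within the limit.

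Section III.c (Exclusion criteria) lists "Habitual binge drinkers, as defined by the consumption of" 4 or more standard drinks a day, or 28 or more drinks a week. Read literally, 4 a day is outside the limit.

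Section III.a (Subjects) says how the lists are used: the 12 participants are enrolled "using the inclusion and exclusion criteria described below". Table 2 in Section V puts "stringent inclusion/exclusion criteria; SASSI and MAST substance abuse screening questionnaires" at the head of the measures taken before enrolment to limit alcohol risk. The Data and Safety Monitoring Plan, under annual safety reports, requires a statement on "whether all participants met entry criteria".

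A neighbouring point concerns body mass index. Section II (Study Rationale and Objectives) describes the aim as to "enroll women with obesity that will undergo a controlled, energy restricted feeding intervention", while Section III.b accepts a BMI of 27 to 50, with a tolerance of 0.5.

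**The concern.** Two lists in one section set a daily drinking limit, and the limits differ at the boundary: one permits 4, the other starts excluding at 4. The value is not remote, because both lines chose it as their boundary and the population must drink daily or almost daily.

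The Protocol relies on its entry criteria as a safeguard against alcohol risk, so a screener should not find two limits. If staff read only the inclusion line, a woman could be enrolled whom the exclusion line bars. The annual report on entry criteria would then seem to have two possible answers for her. In a trial of 12, even one disputed participant would be noticed.

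The BMI wording raises a milder version of the same worry: the objective might describe a narrower group than the one enrolled.

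**Working it through.** No sample size, power or error rate is involved. The check applies the two lists as logical conditions.

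**Inputs**
- Inclusion (Section III.b): weekly total at least 8 and daily number at most 4.
- Exclusion (Section III.c): daily number at least 4, or weekly total at least 28.
- Enrolment (Section III.a): both lists apply, so eligible = inclusion met and exclusion not met.

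**Results for a constant number of drinks per drinking day**

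| Drinks per drinking day | Drinking days per week | Weekly total | Inclusion met | Exclusion met | Eligible |
|---|---|---|---|---|---|
| 1 | 5, 6, 7 | 5, 6, 7 | no | no | no |
| 2 | 5, 6, 7 | 10, 12, 14 | yes | no | yes |
| 3 | 5, 6, 7 | 15, 18, 21 | yes | no | yes |
| 4 | 5, 6, 7 | 20, 24, 28 | yes | yes | no |
| 5 | 5, 6, 7 | 25, 30, 35 | no | yes | no |

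The 5 to 7 days are an assumption about what almost daily means. The Protocol gives no number of days and defines the term by the weekly minimum of 8. At 4 a day, fewer days also reach that minimum: 4 × 2 = 8, 4 × 3 = 12, 4 × 4 = 16. These cases meet both lines through the daily part of the exclusion. The answer is the same: not eligible.

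**Size of the overlap.** At most 4 and at least 4 hold together only at 4. Values between 3 and 4, if averages are used, meet inclusion and not the daily exclusion. The conflict is therefore one point on the scale and not a range.

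**Consistency within the exclusion line.** 28 ÷ 7 = 4, so its weekly and daily parts sit at the same level of intake.

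**What rewording would change.** If the inclusion line were altered only to match the result in the table, the same women would be eligible as now. If the exclusion line were altered instead, eligibility itself would change. Nothing in the design or analysis calls for that.

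**BMI.** The Protocol does not define obesity. If the term meant a BMI of 30 or more (an assumption), the gap would be 30 − 27 = 3 units of the 50 − 27 = 23 unit range. If it meant 27 or more, the gap would be 0. The criterion that decides entry, 27 to 50, is explicit either way.

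**The case for a change.** The strongest case for a change is that the Protocol states no rule of precedence between the lists, so the answer has to be inferred. Even after that inference the inclusion line misstates the ceiling. The wording does not rescue it. *Typically* and *habitual* separate the woman who usually has 2 or 3 drinks and occasionally 4 from the regular 4-a-day drinker, but the regular 4-a-day drinker still fits both lines. Nor does the contrast between drinks and standard drinks help. The only size given is in the 8-Week Dietary Intervention section, where a standard "drink contains roughly 14 grams of pure alcohol", and nothing suggests another size for the inclusion line. Eligibility also belongs in the protocol, so a separate analysis plan could not be expected to settle it.

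All of this stands as a description of the text. It does not show a consequence. An exclusion criterion exists to remove people who would otherwise qualify, so overlap between the lists is ordinary and needs no precedence rule. The argument from the annual report fails for the same reason. The entry criteria are both lists together, and a woman who meets an exclusion has not met them.

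Enrolment on the inclusion line alone is also unlikely. The Screening Visit 1 section requires an interview on substance use and screening questionnaires, after which a multidisciplinary team must approve each candidate. Those steps do not decide which limit applies, but the criteria are not applied by one person reading one line.

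The share of 1 in 12 (8.3%) for a single disputed participant is only the reciprocal of the sample size. It says nothing about how likely the event is.

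**Conclusion.** The inconsistency is real but clerical. The inclusion and exclusion lines meet at exactly 4 drinks a day, and taken together they give one result: such a woman is not eligible. The number enrolled in error is 0 when both lists are applied, which is what Section III.a provides for. No added alcohol exposure, bias, or effect on endpoint, allocation or sample size is shown. Wording that matched the combined lists would enrol the same women, so a change brings no gain beyond tidiness. The two lines can be put in the same terms if the section is opened for another reason. Which limit they should state is for the sponsor.

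This rests on one assumption, that staff apply both lists as Section III.a says. The number of candidates at exactly 4 a day cannot be derived from the Protocol, but the conclusion does not depend on it.

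The BMI point does not hold either. It needs a cut-off that the Protocol does not give, its size may be 0, and the operative range is stated without ambiguity.

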#### **IV. EXPERIMENTAL DESIGN AND METHODS**

All study visits and clinic procedures will be conducted over the course of 1 year at Pennington Biomedical Research Center (PBRC) by trained nurses and research staff in accordance with standard operating and quality control procedures approved by PBRC's Institutional Review Board (IRB). This is a between-subjects parallel study design. All women will undergo a 30% energy restriction for 8-weeks and will be randomized to an ethanol-consuming group or a non-ethanol control group at the start of the study.

Table 1: Schedule of Study Events					
Tests	SV 1	Pre-Rand Visit	CV1	Intervention wk 1- wk 8	CV 2 (wk 8)
Informed Consent/Lifestyle Interview	X				
Height (SV1 only)/Metabolic Weight/BMI, Waist and Hip Circumference, Pulse, and Blood Pressure	X		X		X
Alcohol-related questionnaires (The Short Alcohol Dependence Data, SASSI, MAST)	X			X	
Pedometer Distributed/Collected		X		X (Wk8)	
Food Record/Washout Instructions		X			
Food Record Compliance Check			X		
Medical History/ Physical/ Medications	X				
Medications/Adverse Event Report			X	X(wkly)	X
Fasting Blood Draw*	X†		X*		X*
Questionnaires (retrospective VAS)			X		X
MRI,  H-MRS, FibroScan			X		X
Physical Activity (steps/day)			X		X
Alcohol Tolerance Test		X			
Randomization			X		
Controlled Feeding Dietary Intervention				X	
Body Weight				X	

CV, Clinic Visit; SASSI, Substance Abuse Subtle Screening Inventory; MAST, Michigan Alcoholism Screening Test; VAS, Visual Analogue Scale / †Chem 15, HCG / \*Chem 26, insulin, free and total testosterone and archives

## **Study Visits**

### **Screening Visit 1 (S1)**

SV1 will be conducted the morning after a ~10-hr overnight fast. After acknowledging understanding of the study and all procedures, subjects will sign an informed consent. Demographics, vital signs, and medical history will be assessed. A physical exam will be administered. Anthropometric characteristics (i.e. height, metabolic weight, BMI, blood pressure, waist and hip circumference) will be measured. A blood sample will be collected for laboratory safety tests and menstrual cycle status will be determined.

A semi-standardized Lifestyle (diagnostic) Interview will be administered by trained behavioral staff (Master's Level Psychologists) and overseen by clinical psychologist and Co-Investigator [name]. The interviewer will investigate any current or lifetime prevalence of substance use and will identify and exclude for psychological co-morbidities that preclude participation in the study. Substance Abuse Subtle Screening Inventory (SASSI) and Michigan Alcoholism Screening Test (MAST) questionnaires will be administered. All

participants will be screened and excluded for the presences of diagnosable mood and/ or personality disorders that would interfere with the ability to adhere to protocol. Structured Clinical Interviews (SCID-5 and SCID-5 PD) are semi structured guides to interview that enhance and standardize diagnosis or evaluation of various psychological disorders. The SCID 5 evaluates DSM 5 diagnoses, including mood disorders, psychotic symptoms, psychotic disorders substance use, etc.). The SCID 5 PD is an evaluation of 10 different personality disorders including: Avoidant Personality Disorder, Dependent Personality Disorder, Obsessive-Compulsive Personality Disorder, Paranoid Personality Disorder, Schizotypal Personality Disorder, Schizoid Personality Disorder, Histrionic Personality Disorder, Narcissistic Personality Disorder, and Antisocial Personality Disorder. Test scores from the questionnaires will be thoroughly analyzed by [name] and his team followed by a more detailed discussion with the subject. Participants that display any characteristics of substance abuse or mental disorders will be excluded. The interview will also ascertain barriers to participation in the study, including participants' willingness to commit to the study, potential scheduling conflicts, support from household members to participate in the study, motivation and challenges facing the participant, details of the randomization and intervention, and other study-related issues of importance. This information will be used to identify and exclude from enrollment participants who will not be capable of completing the study. The results from the diagnostic interview will be used to provide an overall eligibility assessment for each candidate. A multidisciplinary team consisting of behavioral experts, dietitians, clinical staff, Medical Investigator ([name]), and study staff will discuss and approve a candidate for official admission to the study. If eligible, the participants will undergo a Pre-Randomization Visit, which will include a mandatory one-night test of ethanol consumption at the proposed dose to assess alcohol tolerance.

#### Pre-Randomization Visit

Before enrollment in the study, all women will be required to undergo an overnight alcohol tolerance test at the required ethanol dose. Participants will receive the required ethanol dose at the pre-randomization visit along with instructions for consumption. Participants will be monitored via video chat technology (Skype) by study staff from the time the person starts drinking to 1-2 hours after they have finished drinking the alcohol. For minor adverse events experienced by the subject, such as headache, nausea, diarrhea or other similar issue, that are conveyed to the study staff, one should call the medical investigator. In the unlikely event that the person experiences serious adverse events and becomes agitated and destructive, or otherwise being out of control and a danger to herself and others, or if the person becomes so sedated that she is no longer responding to conversation in the audio portion of the Skype and is becoming unconscious, these would be indications to call 911. Women will be instructed to do a one-week alcohol-free washout. Women will be administered a dietary record and step log (pedometer provided) and asked to return these completed items at Clinic Visit 1. Pending adherence to the overnight alcohol test, the one-week ethanol-free washout, and the return of a dietary record, participants will undergo Clinic Visit 1.

#### Clinic Visit (CV) 1 and 2

At CV1 and 2, women will report to PBRC after an overnight fast during the luteal phase of the menstrual cycle. Anthropometric characteristics will be measured. Body composition scans (MRI, H-MRS, and FibroScan) and blood draws (Chem 26, insulin, testosterone (free and total)) will be performed. A sample of blood (serum and plasma) will be collected for archive. The appetite questionnaire will be administered. Participants will be randomized to the control or ethanol group and begin the dietary intervention.

